Protocol

Project Title: Persistent Inflammation, Immunosuppression and Catabolism Syndrome (PICS): A New Horizon for Surgical Critical Care

Subtitle. Kidney Response to Sepsis Affects Angiogenic Balance and Likelihood of CCI and PICS

2. Investigator(s):

[name]., Ph.D.

[name].

[name].

[name].

3. Abstract:

Approximately a third of those patients who survive an early sepsis episode linger in the intensive care unit with manageable organ dysfunction without meeting criteria for established late multi-organ failure. Their clinical course is characterized by ongoing protein catabolism with poor nutritional status, poor wound healing, and recurrent infections. These patients are commonly discharged to long-term, acute care facilities, but due to excessive loss of lean body mass and their immunosuppressed state, they often develop secondary nosocomial infections and are rarely able to return to a fully functional state. The overall hypothesis of this program grant is that persistent inflammation, immunosuppression and catabolism (PICS) are the hallmark of pathophysiologic processes leading to a decrease in long-term survival and functional capacity in patients with chronic critical illness. This study investigates the mechanism by which kidney dysfunction perpetuates inflammation, immunosuppression, and catabolism in chronic critical illness. In a prospective, longitudinal, case-control study of sepsis patients with one year follow-up using iohexol clearance we will measure glomerular filtration rate in patients with chronic critical illness and controls (sepsis patients discharged from ICU before day 14) to determine to what extent degree of kidney dysfunction contributes to decreased survival and increase in chronic kidney disease at year one after sepsis onset.

4. Background:

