Approximately a third of those patients who survive an early sepsis episode linger in the intensive care unit with manageable organ dysfunction without meeting criteria for established late multi-organ failure. Their clinical course is characterized by ongoing protein catabolism with poor nutritional status, poor wound healing, and recurrent infections. These patients are commonly discharged to long-term, acute care facilities, but due to excessive loss of lean body mass and their immunosuppressed state, they often develop secondary nosocomial infections and are rarely able to return to a fully functional state. The overall hypothesis of this program grant is that persistent inflammation, immunosuppression and catabolism are the hallmark of pathophysiologic processes leading to a decrease in long-term survival and functional capacity in patients with chronic critical illness. This study investigates the mechanism by which kidney dysfunction perpetuates inflammation, immunosuppression, and catabolism in chronic critical illness. We will test the working hypothesis that persistent kidney dysfunction in sepsis associated chronic critical illness contributes to decreased survival through the development of persistent inflammation, immunosuppression and catabolism. In chronic critical illness, the persistence of inflammatory state may lead to capillary rarefaction in the kidney causing accelerated chronic kidney disease. Progression of chronic kidney disease during chronic critical illness can drive persistent inflammation, immunosuppression and catabolism. Indeed, many of the features of chronic critical illness are consistent with the protein-energy malnutrition and muscle wasting associated with chronic kidney disease. Thus the kidney can play a contributory role in chronic critical illness and PICS, respectively.

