The goal of this study is to determine to what extent persistent kidney dysfunction contributes to inflammation, catabolism and long-term mortality in chronic critical illness. We will test the working hypothesis that persistent kidney damage in chronic critical illness contributes to decreased survival through persistent inflammation, immunosuppression and catabolism.

6. Research Plan:

Study overview and design

This is a prospective, longitudinal, case-control study involving a subset of the initial cohort of 400 sepsis subjects enrolled in IRB STUDY #2014-611 who agree to measurement of glomerular filtration rate using iohexol clearance and the amended measurements listed above. Assuming a minimum 70% recruitment rate, we expect to enroll minimum of 230 patients and maximum of 400.

Identifying patients and consent

All sepsis patients who consent to enroll in the IRB Project #2014-611 and meet inclusion/exclusion criteria will be asked for enrollment in this study after they are consented for the IRB Project #2014-611. The informed consent will be obtained by the same research staff

within the Human Subject Core of the University of Florida P50 Center. Since many sepsis patients in the surgery and trauma ICUs may have altered mental status or pharmacologic sedation, but would be regarded as prospective research subjects a legal authorized relative (LAR) or next of kin would be approached for informed consent. The research nurse will monitor the patient's progress and once they regain capacity, the patient will be reconsented.

Inclusion Criteria

- a) Presence in the surgery or trauma ICU where clinical care can be managed by surgical critical care guided by standard operating procedures.
- b) Age of ≥ 18 years
- c) First entrance into our sepsis protocol at Shands/UF on index admission.
- d) Ability to obtain informed consent.

Exclusion criteria

Expected lifespan of the patient is less than 3 months due to severe pre-existing comorbidities (ex. recurrent, advanced or metastatic cancer).

- b) Severe traumatic brain injury (evidence of neurologic injury on CT scan and a GCS <8)
- c) refractory shock (i.e., patients who die within 12 hours)
- d) uncontrollable source of sepsis (e.g., irreversible disease state such as unresectable dead bowel)
- e) Patient or patient's family are not committed to aggressive management of the patient's condition.
- f) severe CHF (NY Heart Association Class IV)

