The patients will be asked to return for a one year follow up appointment that will occur with the one year appointment from IRB protocol #2014-611 at the Institute on Aging. The patients will receive a \$25 compensation for the inpatient portion of the study and a \$75 compensation for their time when they return for the one year follow up visit. At one year follow-up all measurements for iohexol clearance, will be performed in CTSI. Timed urine collection at one year follow up will be performed at home and all necessary supplies will be mailed to patient. If the patient did not do a timed collection, but is still willing to perform timed urine at the time of the CTSI visit, we will time the urine collection during their CTSI visit. For patients who opt only for serum creatinine/cystatin C measurement and spot urine microalbumin/creatinine ratio, urine and blood will be collected in the CTSI as a part of the IRB protocol #2014-611.

Primary Outcomes

We will compare:

Protocol

IRB version 03.09.04

PI version 9/10/2015

- a) The decline in glomerular filtration rate at 1-year follow-up between chronic critical illness and control groups.
- b) Correlation between iohexol glomerular filtration rate and estimated glomerular filtration rate using previously validated equation applied to serum creatinine.
- c) Development of de novo albuminuria or progression of existing albuminuria.

Data Collection and Analyses

All relevant clinical and laboratory variables for this cohort will be uploaded directly into the REDCap case report form (CRF) from the EPIC EMR for the main STUDY IRB#2014-611.

Sample size and feasibility. Assuming that chronic critical illness patients have at least a two-fold decline in glomerular filtration rate as compared to the average glomerular filtration rate decline of 6 ± 16 ml/yr, the sample size of 150 chronic critical illness and 80 control subjects will offer 80% power at a two-sided significance of $P=0.05$.

Data analyses and interpretation. The parametric and non-parametric tests for difference between two independent samples will be used to compare decline in glomerular filtration rate between chronic critical illness. Using the Cox survival model we will test the multivariate relationship between glomerular filtration rate at day 14 and survival status at year 1.

Protection of Privacy and Confidentiality

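### The enrolment and power figures disagree: 70% of 400 is 280 rather than 230, 150:80 gives about 77% power rather than 80%, and nothing is allowed for loss before one year

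*Combined protocol and SAP*

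**What the plan says.** Section 6, Study overview and design, describes the study population as "a subset of the initial cohort of 400 sepsis subjects enrolled in IRB STUDY #2014-611" and continues: "Assuming a minimum 70% recruitment rate, we expect to enroll minimum of 230 patients and maximum of 400".

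The Sample size and feasibility paragraph says that "the sample size of 150 chronic critical illness and 80 control subjects will offer 80% power" at a two-sided 0.05 level. The assumption is that CCI patients have "at least a two-fold decline in glomerular filtration rate" relative to an "average glomerular filtration rate decline of 6 ± 16 ml/yr".

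Primary outcome (a) is the GFR decline at one-year follow-up, compared between CCI patients and controls. The Abstract defines the comparison group as "controls (sepsis patients discharged from ICU before day 14". The only figure on the expected size of the CCI group is in the Abstract and Background: "Approximately a third of those patients who survive an early sepsis episode linger in the intensive care unit". No quota, matching or enrichment is described, and no retention rate is given.

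**The concern.** Four planning figures should follow from one another: the cohort of 400, the 70% rate, the minimum of 230 and the 150:80 split. They do not.

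- **Enrolment.** The rate and the cohort give a different minimum from the one stated.
- **Loss.** The stated minimum to enrol is the same number that the power statement needs at analysis. An analysed patient must be alive and measured at one year. The protocol expects some not to be: it plans a Cox model for survival to year 1 and lists death among the anticipated events in its safety monitoring plan.
- **Power.** The stated 80% should be reproducible from the stated difference, SD, group sizes and significance level.
- **Split.** A design with nearly two CCI patients per control does not fit the protocol's own description, in which CCI patients are the minority.

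At stake is whether a reader can tell what power the primary comparison has.

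**Working it through.** **Inputs.** From the Sample size and feasibility paragraph: control decline 6 ml/yr; CCI decline twice that, 12 ml/yr, so the difference is 6; SD 16, reading the ± figure as an SD common to both groups; 150 CCI and 80 control; two-sided 0.05. From Study overview and design: cohort 400, rate 70%, minimum 230, maximum 400. From the Abstract and Background: CCI share about one third. Loss rates are my assumptions.

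**1. The plan's own power.** The standard error of the difference is 16 × √(1/150 + 1/80) = 16 × √0.019167 = 2.215. The standardised difference is 6 / 2.215 = 2.709. The normal approximation gives Φ(2.709 − 1.960) = Φ(0.749) = 77.3%. The two-sample t-test (noncentral t) gives 77.0%. The stated 80% is not reproduced. A rank test at an assumed relative efficiency of 0.955 gives 75.4%. An equal split, 115:115, would give about 81%, but that is not the stated split.

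**2. Size needed at that ratio.** With ratio 150/80 = 1.875, controls = (1 + 1/1.875) × 16² × (1.960 + 0.842)² / 6² = 1.533 × 55.81 = 85.6, so 86. CCI = 1.875 × 86 = 161.25, so 162. The total is 248.

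**3. Enrolment.** 0.70 × 400 = 280. 230 / 400 = 57.5%. 150 + 80 = 230, which is the stated minimum.

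**4. Loss from 230 at the stated split (t-test).** With 10% loss, 135:72 gives 72.5%. With 20% loss, 120:64 gives 67.4%.

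**5. Split.** One third of 230, 280 and 400 is about 77, 93 and 133. Obtaining 150 CCI patients needs a share of 150/230 = 65.2%, 150/280 = 53.6% or 150/400 = 37.5%.

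**6. Power at a one-third share (t-test).**

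| Enrolled | No loss | 10% loss | 20% loss |
|---|---|---|---|
| 230 | 77:153, 76% | 69:138, 72% | about 67% |
| 280 | 93:187, 84% | 84:168, 80% | 75:149, 75% |
| 400 | 133:267, 94% | 120:240, 92% | 107:213, 88% |

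At 400 enrolled, power is 84% with 30% loss (93:187) and 78% with 40% loss (80:160).

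**The case against.** A reader might infer something stronger: that the cohort cannot supply 150 CCI patients even at 400 enrolled, and that the stated power therefore rests on an unattainable sample. The documents do not support this, for three reasons.

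- The one-third figure is approximate. It is background text about survivors of early sepsis, not a planning assumption for this cohort, which has its own exclusions. A share of 37.5% would give 150 of 400. Even if the true share were exactly one third, the chance of 150 or more among 400 is about 4%. The mismatch is clear only at 230 and 280.
- With a common SD, power depends on 1/n₁ + 1/n₂, so it does not matter which group is larger. Moving from 150:80 to 77:153 costs less than one percentage point. The CCI share is not what weakens the power.
- Correcting the figures need not make the study look worse. If 280 are enrolled, power is above 80% before loss and about 80% after 10% loss. At 400 it stays above 80% up to 30% loss.

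Two readings might rescue the 230. It could mean completers out of 280 (230/280 = 82% retention), but the text speaks of enrolment and gives no retention rate. Or the 70% could apply to about 329 eligible patients (230/0.70), but no such base is stated and it sits poorly with a maximum of 400. It is also fair to say that a floor of 230 is met by 280, so the enrolment slip does not by itself threaten power.

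The objection removes the claim of impossibility and any claim that the CCI share harms power. It does not remove the unexplained 230, the missing loss allowance or the 80% that should read 77%.

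**Conclusion.** The planning figures are inconsistent and one stated result is wrong. The stated inputs give about 77% power at 150:80, three points below the stated 80%, and about 248 analysed patients at that ratio would be needed. The enrolment minimum is 50 below what 70% of 400 gives, and it equals the analysed number with nothing in reserve for one-year loss. At that minimum and split, assumed losses of 10% and 20% leave 72.5% and 67% power. The 150:80 split is unsupported by anything in the protocol, but this is a gap in explanation with almost no effect on power.

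Across the totals that the protocol's figures allow, power before loss runs from 76% (230 at one third CCI) to 94% (400 at one third), so the plan does not tell the reader what power to expect. These results take the ± 16 as a common SD and the two-fold decline as 12 against 6. The counts by group at one third carry a background figure over to the enrolled subset, and all loss rates are assumed.

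**What to change.** Four changes to the text, with no added patients or procedures:

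1. In Sample size and feasibility, correct the power for 150:80 from 80% to 77%.
2. In Study overview and design, restate the expected minimum as 280 if 70% of 400 stands; otherwise state the base that yields 230. The rate should not simply be changed to 57.5% to match the total, since nothing in the protocol supports that rate.
3. Justify 150:80, or replace it with the split the investigators expect and give its source. The 93:187 used above illustrates one third of 280 and should not be adopted as a design parameter without support.
4. State a one-year allowance for death and loss, and report power after it. As a template under assumed losses, 280 enrolled at about 93:187 gives 84% with none, 80% at 10% and 75% at 20%.

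The cost is a short revision of two paragraphs. The reported power may fall or rise, depending on the total and the loss allowance adopted.

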The main goal of this project is to measure kidney filtration function at day 14 of the ICU stay or the day of discharge from the ICU (whichever occurs first), in order to determine the presence and *magnitude of persistent kidney dysfunction after sepsis episode and to longitudinally assess* further decline of kidney function at one year follow-up. In our initial IRB protocol we have proposed to use iohexol clearance as a gold standard that provides most accurate determination of glomerular filtration rate (GFR). Unfortunately we have not been able to recruit patients into the study as designed due to the complexity of this procedure and need for a dedicated IV line. Since one of the main goals of the overall project is to determine the decline in glomerular filtration rate from the sepsis episode to the one year follow up, we have considered different approaches, in order to be able to obtain this valuable data.

We propose to offer patients four complementary ways for GFR assessment, both at approximately day 14 or approximately at the day of discharge from the ICU and at the one year follow up :

1. Determine clearance of iohexol from blood after iohexol injection and/or
2. Determine appearance of iohexol in urine after iohexol injection (this would be the same injection as in one, and would not require two injections) and/or
3. A timed urine collection to determine clearance of urea and creatinine and/or
4. Estimated GFR using calculations with serum creatinine, if performed clinically if not we will draw it specifically for the study, and cystatin C, performed specifically for the study. Currently any patient that is enrolled in this protocol will already be a part of IRB201400611 and will already be getting serum creatinine, cystatin C and a urine microalbumin/creatinine ratio drawn at the one year appointment.

This approach will allow us to maximize recruitment of patients into the study by providing flexibility, but it also provides an important opportunity to validate the different measurements against the gold standard, iohexol clearance. For all patients we will also obtain a urine microalbumin/creatinine ratio as another important determinant of structural kidney damage.

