We also propose to include stage 3 AKI patients on renal replacement therapy, who were previously excluded. Some of these patients do recover after initial episode and will present at one year follow up. It will be very valuable for us to understand factors leading to recovery. For these patients we will use only methods 2 and/or 3 for estimation of GFR, both of which are safe. Even patients who are dialysis dependent have some level of residual renal function and even if they make even a minimal amount of urine this may be an important determinant of renal recovery.

The assessments will be performed approximately 72 hours within day 14 or the anticipated discharge from the ICU and at 1 year follow-up.

Given the loss of muscle mass in chronic critical illness, we will measure, rather than estimate glomerular filtration rate, to determine whether unrecognized kidney dysfunction in late sepsis drives inflammation and catabolism, contributing to poor long term survival and development of chronic kidney disease. For the assessment of glomerular filtration rate, the most frequently used clinical test is serum creatinine, despite the fact that its accuracy depends on a constant muscle mass, which is almost never the case with patients with chronic critical illness. We have previously demonstrated that sepsis and chronic critical illness are associated with a rapid and significant loss of lean muscle mass over time. Even a small fall of 25% in muscle mass should lead to a fall in serum creatinine of 25%. Thus in a chronic critical illness patient hospitalized for 4 weeks, the persistent increase in serum creatinine from a baseline of 1.0 mg/dl to 1.5 mg/dl implicates a significant drop in glomerular filtration rate; assuming a 50% reduction in muscle mass, in this individual a serum creatinine of 1.5 would reflect glomerular filtration rate of ~ 37 mL/min/1.73 m², consistent with stage 3 chronic kidney disease. To determine whether unrecognized decline in kidney function contributes to persistent inflammation, decreased protein intake, and muscle wasting in chronic critical illness it is necessary to measure glomerular filtration rate rather than estimate it.

5. Specific Aims:

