- g) Child-Pugh Class C liver disease or pre-liver transplant.
- h) known HIV infection with CD4 count <200 cells/mm 3
- i) organ transplant recipient on immunosuppressive agents
- j) known pregnancy and mother's that are breastfeeding
- k) prisoners
- l) Institutionalized patients
- m) inability to obtain informed consent.
- n) Chemotherapy or radiotherapy within 30 days prior to sepsis.
- o) End stage renal disease on admission

Determination of Glomerular Filtration Rate and Proteinuria

For all patients we will measure and estimate GFR and urinary microalbumin/creatinine ratio at day 14 of ICU admission or at hospital discharge (if prior to day 14) and one year follow-up.

We propose to offer patients four complementary ways for GFR assessment, both at approximately day 14 or approximately at the day of discharge from the ICU and at the one year follow up :

1. Determine clearance of Iohexol from blood after Iohexol injection and/or
2. Determine appearance of Iohexol in urine after Iohexol injection (this would be the same injection as in 1 and would not require another injection).
3. A timed urine collection to determine clearance of urea and creatinine and/or
4. Estimated GFR using calculations with serum creatinine, if performed clinically, if not we will draw specifically for the study, and cystatin C, performed specifically for the study. Currently any patient that is enrolled in this protocol will already be a part of

IRB201400611 and will already be getting serum creatinine, cystatin C and a urine microalbumin/creatinine ratio drawn at the one year appointment.

For all patients we will also obtain urine microalbumin/creatinine ratio as another important determinant of structural kidney damage. If a patient is of childbearing potential at the one year follow up appointment, they will be given a pregnancy test. If they test positive, they will not be given the iohexol injection.

1. Iohexol clearance.

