Iohexol clearance will not be performed in patients with a known allergy to contrast. All patients will need two IVs for this procedure. If the subject does not have 2 intravenous catheters (IVs) as a part of their routine clinical care during sepsis episode they will be placed by someone from the research team. We will attempt to place a 22 gauge or larger IV as indicated by the patients veins. We will inject iohexol 0.5-1 ml of iohexol diluted in normal saline through an existing IV catheter, and we will collect no more than 3 ml of blood prior to the injection and at approximately 1, 2, 3 and 4 hours after injection. The concentration of iohexol in the blood will be measured by ELISA (Biopal Inc). The GFR will be calculated by the blood clearance method:

The concentration of iohexol ($\mu\text{g}/\text{ml}$) in each blood sample will be plotted as a function of time. The data will be fit to a one exponential decay function, i.e., $Y = B e^{-bX}$. The function will be integrated over the limits zero to infinity to obtain the area-under-the-curve (AUC), i.e., $AUC = B/b$ ($\text{mg}\cdot\text{min}/\text{ml}$). The GFR value (ml/min) is then obtained by dividing the administrated dose by the AUC (REF:

2. Timed urinary collection for combined urea and creatinine clearance.

The urine will be collected for at least 4 hours to as long as 24 hours or more. The urine volume determined and a sample sent to the lab for determination of creatinine and urea concentration. We will not place a foley if there is not a foley and the person will only be asked to collect their urine for the indicated time.

3. Estimation of GFR using serum creatinine and cystatin C. We will estimate GFR using both serum creatinine and cystatin C and average the two values using CKD-EPI equation.

The glomerular filtration rate at 1 year will be compared to the measured glomerular filtration rate at discharge and the rate of change in glomerular filtration rate over time will be determined. The measured iohexol glomerular filtration rate will be compared to the estimated glomerular filtration rate, as determined by the in order to correlate the equation after adjusting for loss of muscle mass.

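### Urinary iohexol (GFR method 2) has no procedure, assay or formula, and without paired blood samples it fixes only the ratio of GFR to distribution volume

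*Combined protocol and SAP*

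**What the plan says.** Section 4 (Background) and section 6 (Determination of Glomerular Filtration Rate and Proteinuria) offer patients four ways of assessing GFR, at about day 14 or ICU discharge and again at one year. In section 4 the first reads "Determine clearance of iohexol from blood after iohexol injection and/or". In section 6 the second reads "Determine appearance of Iohexol in urine after Iohexol injection (this would be the same injection as in 1 and would not require another injection". In both lists *and/or* stands between the two.

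Section 4 also admits patients with stage 3 AKI on renal replacement therapy (RRT) and states: "For these patients we will use only methods 2 and/or 3 for estimation of GFR, both of which are safe". Read against the list just before it, this means urinary iohexol and/or timed urine, without blood clearance.

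The procedures in section 6 describe three methods, not four:

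- **1. Iohexol clearance.** "The concentration of iohexol in the blood will be measured by ELISA (Biopal Inc"). The only iohexol formula is for blood: "The GFR value (ml/min) is then obtained by dividing the administrated dose by the AUC".
- **2. Timed urinary collection.** The analytes named do not include iohexol: "The urine volume determined and a sample sent to the lab for determination of creatinine and urea concentration". The collection time for this method is wide: "The urine will be collected for at least 4 hours to as long as 24 hours or more".
- **3. Estimation of GFR** from serum creatinine and cystatin C.

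Urinary iohexol has no collection window, assay or formula in any section.

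**The concern.** Method 2 is presented as a way to obtain a GFR, but the plan does not say how. The gap is more than missing detail. The amount of tracer that reaches the urine reflects both how fast the kidney clears it and how diluted it is in the body. Without plasma concentrations over the same interval, the two cannot be separated.

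This matters because decline in GFR is primary outcome (a) and iohexol GFR is one side of the correlation in primary outcome (b). Fluid volume may well differ between an ICU assessment and a visit one year later, and may change differently in patients with chronic critical illness (CCI) and in controls. A urine-only value treated as a GFR would carry that difference. A patient assessed by method 2 alone would also have received an injection, which the data and safety monitoring plan ties to more than minimal risk, without obtaining a usable measured GFR from it.

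The numbering conflict adds to this. Method 2 is urinary iohexol in the four-method lists, but heading 2 of the procedures is the urea and creatinine collection. What RRT patients are to receive therefore depends on which numbering is read.

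**Working it through.** The documents give no figure on this point to reproduce. The check uses the protocol's own model.

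**Inputs**

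- From section 6, Iohexol clearance: concentration Y = B·e^(−bX), AUC = B/b, GFR = dose/AUC.
- From section 4: the protocol's example GFR of about 37 (given per 1.73 m², treated here as ml/min).
- Assumed: a 4 h collection (240 min). None is stated for urinary iohexol; blood sampling ends at about 4 h.
- Assumed: distribution volume V of 12 to 25 L, with 30 L in one example. The documents give none.
- Assumed: renal elimination only and complete urine collection, except in step 6.

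**Step 1. What urine alone measures.** With B = dose/V, GFR = dose/AUC gives b = GFR/V. The fraction excreted by time t is

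F(t) = 1 − exp(−GFR·t/V).

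GFR and V enter only as a ratio. For example, GFR 30 with V 15 L gives 30 × 240/15,000 = 0.48, and GFR 60 with V 30 L gives 60 × 240/30,000 = 0.48. Both excrete 1 − e^(−0.48) = 38.1%.

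**Step 2. Reading one result back.** For 45% excreted in 4 h, GFR = −ln(0.55) × V/240 = 0.002491 × V (V in ml):

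| Assumed V | GFR consistent with 45% excreted |
|---|---|
| 12 L | 29.9 ml/min |
| 15 L | 37.4 ml/min |
| 20 L | 49.8 ml/min |
| 25 L | 62.3 ml/min |

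**Step 3. Change over time.** If one fixed volume V₀ were used for conversion, apparent GFR = true GFR × V₀/V. Take a constant true GFR of 37 and a true volume falling from 20 L to 15 L:

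- V₀ = 15 L: 37 × 15/20 = 27.75 at index and 37 at one year, an apparent rise of 9.25 ml/min.
- V₀ = 20 L: 37 at index and 37 × 20/15 = 49.3 at one year, an apparent rise of 12.3 ml/min.

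An error in this direction would hide a true decline.

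**Step 4. A longer collection does not help.** At 24 h (1,440 min) and V = 15 L, excretion is 94.4% at GFR 30 and 99.7% at GFR 60. Almost the whole dose is recovered either way.

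**Step 5. Paired plasma removes the problem.** The amount excreted is U(t) = dose × F(t), and AUC(0–t) = (dose/GFR) × F(t). Their ratio U/AUC equals GFR whatever V is. Computed at GFR 37, it returns 37 ml/min at both 15 L and 30 L.

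**Step 6. RRT.** If dialysis also removes iohexol with clearance K, urinary excretion is dose × GFR/(GFR + K) × [1 − exp(−(GFR + K)t/V)]. With assumed GFR 10, V 25 L and 24 h, this is 44% of the dose at K = 0, 25% at K = 25 ml/min and 19% at K = 40 ml/min. Urine alone then mixes GFR with dialysis removal as well as volume.

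**Step 7. Effect on outcome (a).** Bias in the group contrast is roughly (share on method 2 alone × mean shift) in CCI minus the same product in controls. A volume change common to both groups largely cancels if shares and GFR levels are similar. As an illustration with assumed inputs, take a share of 5% to 20% in both groups and a shift of about 12 ml/min of which half differs between groups: 12 × 0.5 × 0.05 = 0.3 and 12 × 0.5 × 0.20 = 1.2 ml/min.

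**The case against.** Four points can be made for the plan.

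1. *Silence is not a decision.* A reader might infer that no urine iohexol assay is planned. The documents do not say so. Undertaking to determine iohexol in urine implies measuring it, and the sentence on creatinine and urea belongs to the separate timed collection. This stands: the supported statement is that the method is unspecified.
2. *Method 2 may never be used alone.* It shares method 1's injection, and the only injection procedure draws blood before injection and at about 1, 2, 3 and 4 h. This stands in part. The *and/or* wording still permits urine alone, and the RRT sentence in section 4 leaves method 1 out.
3. *Nobody proposes a fixed-volume conversion.* A reader might infer that the primary contrast is biased by twice the 6 ml/yr difference for which the study is sized. The documents do not support this. No section converts excretion with an assumed volume or says that a urine-only value enters outcome (a) or (b). The 9 to 12 ml/min in step 3 is a within-patient error at assumed volumes and cannot be set against a between-group difference.
4. *Other GFR data exist.* A reader might infer that patients on method 2 alone contribute nothing. That goes too far: creatinine and cystatin C are collected at one year through the parent study, so estimated GFR remains a fallback, although section 4 argues that GFR should be measured rather than estimated in this population.

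These points limit the likely harm. None of them makes urine-only iohexol excretion a valid GFR.

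**Conclusion.** The concern holds as a defect in a stated method. Method 2 is offered as a GFR assessment that may be used without blood clearance, it has no procedure, assay or formula, and in that form it cannot yield a GFR. The algebra rests on the protocol's one-exponential model, renal elimination only and complete urine collection. The ml/min figures also rest on assumed volumes and a 4 h window: one excretion result spans about 30 to 62 ml/min across 12 to 25 L.

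No bias in outcome (a) is demonstrated. Its size would depend on the between-group difference in volume change and on the share of patients with method 2 alone, and the documents state neither. The mismatch in method numbering is a separate, plain inconsistency that must be reconciled.

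**What to change.** Choose one of two changes in sections 4 and 6.

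- **Delete method 2 as a stand-alone GFR method.** This is the simpler course, because a patient with method 1 blood samples already has an iohexol GFR.
- **Define it as urinary iohexol clearance.** Assay iohexol in urine, collect urine over the same interval as the blood samples, and compute amount excreted divided by plasma iohexol AUC over that interval. Replace *and/or* so that method 2 is used only with the method 1 blood samples.

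Under either change, state that urine-only excretion is not entered as a GFR in outcome (a) or (b).

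Use one numbering for the methods across the two lists, the RRT sentence and the procedures, and state what methods 2 and 3 mean for patients on RRT. The choice of methods for them is the sponsor's.

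**Cost.** Deletion needs only wording. The second option adds one urine iohexol assay per session, whose availability must be confirmed because only a blood ELISA is named. Since the first post-injection blood sample is at about 1 h, an AUC from time zero also relies on extrapolating the fitted curve back. Under either option, patients who would accept only urine sampling after the injection move to timed urine or estimated GFR, which gives back some of the flexibility that the four-method list was meant to provide.
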